5.6 Concomitant and post-study treatment(s)

5.6.1 Olaparib and CYP3A4

The use of any natural/herbal products or other “folk remedies” should be discouraged but use of these products, as well as use of all vitamins, nutritional supplements and all other concomitant medications must be recorded in the eCRF.

Olaparib is an investigational drug for which no data on in vivo interactions are currently available. Based on in vitro data and clinical exposure data, olaparib is considered unlikely to cause clinically significant drug interactions through inhibition or induction of cytochrome P450 enzyme activity. In vitro data have, however, also shown that the principal enzyme responsible for the formation of the 3 main metabolites of olaparib is CYP3A4 and consequently, although the contribution of metabolic clearance to total drug clearance in man is currently unknown, to ensure patient safety, the following potent inhibitors of CYP3A4 must not be used during this study for any patient receiving olaparib.

While this is not an exhaustive list, it covers the known potent inhibitors, which have most often previously been reported to be associated with clinically significant drug interactions:

- Fluvoxamine, fluconazole, fluoxetine, amiodarone, paroxetine, quinidine, ketoconazole, itraconazole, ritonavir, idnavir, saquinavir, telithromycin, clarithromycin

For patients taking any of the above, the required wash-out periods prior to starting olaparib are:

- Fluoxetine - 5 weeks; paroxetine - 2 weeks; any of the others - 1 week wash-out period

In addition, to avoid potential reductions in exposure due to drug interactions, the following CYP3A4 inducers are excluded:

- Phenytoin, rifampicin, rifapentin, rifabutin, carbamazepine, phenobarbitone, and St John’s Wort

For patients taking any of the above, the required wash-out periods prior to starting olaparib are:

- phenobarbitone 5 weeks, and for any of the others, 3 weeks.

If the use of any potent inducers or inhibitors of CYP3A4 are considered necessary for the patient’s safety and welfare during the course of the study, the investigator must contact the AstraZeneca Study Physician. A decision to allow the patient to continue in the study will be made on a case-by-case basis.

5.6.2 Other Concomitant Medications

Any medications, with the exceptions noted in Section 5.6.5 below, which are considered necessary for the patient's welfare during the study, and which it is believed will not interfere with the study medication, may be given at the discretion of the investigator, providing the medications, the doses, dates and reasons for administration are recorded in the eCRF.

In addition, any unplanned diagnostic, therapeutic or surgical procedure performed during the study period must be recorded in the comments section of the corresponding Adverse Event report.

Anticoagulant Therapy: Patients who are taking warfarin may participate in this trial; however, it is recommended that prothrombin time (INR and APTT) be monitored carefully at least once per week for the first month, then monthly if the INR is stable. Subcutaneous heparin is permitted.

Anti-emetics/Anti-diarrhoeals: Prophylactic anti-emetics and/or anti-diarrhoeals will not routinely be given. Should a patient develop nausea, vomiting and/or diarrhoea, which, in the investigator's opinion, is considered related to the study medication, then appropriate prophylactic treatment may be given.

The reason(s) for the use, doses and dates of treatment should be recorded in the patient's medical records and appropriate section of the eCRF.

All medications (prescriptions or over-the-counter medications) continued at the start of the trial or started during the trial or until 30 days from the end of the last protocol treatment and different from the trial medication must be documented.

5.6.3 Palliative radiotherapy

Palliative radiotherapy may be used for the treatment of pain at the site of bony metastases that were present at baseline, provided the investigator does not feel that these are indicative of clinical disease progression during the study period.

5.6.4 Administration of other anti-cancer agents

Patients must not receive any other concurrent anti-cancer therapy, including investigational agents, while on study treatment. Patients may continue the use of bisphosphonates for bone disease and corticosteroids provided the dose is stable before and during the study and they were started at least 4 weeks prior to beginning study treatment. Patients with hormone-refractory prostate cancer may continue with LHRH agonist treatment if, in the investigator's opinion, it is appropriate.

5.6.5 Medications that may NOT be administered

No other chemotherapy, immunotherapy, hormonal therapy or other novel agent is to be permitted while the patient is receiving study medication.

Other medication, which is considered necessary for the patient's safety and well being, may be given at the discretion of the investigator and recorded in the appropriate sections of the CRF.

5.7 Treatment compliance

The administration of all medication (including investigational products) should be recorded in the appropriate sections of the eCRF.

Patients should be given clear instructions on how and when to take their study treatment. Patients will self-administer olaparib. Compliance of the first dose and dose taken on the day of any study visit of olaparib will be assured by supervised administration by the investigator or delegate. Study site staff will make capsule counts at regular intervals during treatment, ideally at the patient's monthly visits. Compliance will be assessed by the capsule count and the information will be recorded in the appropriate section of the eCRF. After the capsule count has been performed, the remaining capsules will not be returned to the patient but will be retained by the study site until reconciliation is completed by the study monitor. All patients must return their bottle(s) of olaparib at the appropriate scheduled visit, when a new bottle(s) will be dispensed. Patients will be instructed to notify study site personnel of missed doses. Dates of missed or held doses will be recorded on the eCRF.

Patients must return all containers and any remaining capsules at the end of the study.

5.7.1 Accountability

The study drug provided for this study is for use only as directed in the study protocol. It is the investigator/institution's responsibility to establish a system for handling study treatments, including investigational medicinal products, so as to ensure that:

- Deliveries of such products from AstraZeneca are correctly received by a responsible person
- Such deliveries are recorded
- Study treatments are handled and stored safely and properly as stated on the label
- Study treatments are only dispensed to study patients in accordance with the protocol.

The study personnel will account for all study medications dispensed and returned.

At the end of the study, it must be possible to reconcile delivery records with records of usage and destroyed/returned stock. Records of usage should include the identification of the person to whom the study treatment was dispensed, the quantity and date of dispensing and unused study treatment returned to the investigator. This record is in addition to any drug accountability information recorded on the eCRF. Any discrepancies must be accounted for

on the appropriate forms. Certificates of delivery and return must be signed, preferably by the investigator or a pharmacist, and copies retained in the investigator site file.

5.8 Discontinuation of investigational product

Patients may be discontinued from investigational product(IP), olaparib, in the following situations:

- Patient decision. The patient is at any time free to discontinue treatment, without prejudice to further treatment
- Adverse Event
- Severe non-compliance with the study protocol
- Any CTC grade 3 or 4 events that have not reverted to CTC grade 1 or less within 4 weeks (28-days). At the investigator's discretion, following dose interruption, patients may be considered for dose reductions providing they have not already undergone the maximum number of dose reductions allowed for guidelines see section 5.5.6. However, if upon re-challenging with olaparib at the lowest reduced dose, 100 mg bd (for guidelines refer to Section 5.5.6), any CTC grade 3 or 4 adverse events recur, the patient must be discontinued.
- Objective progression according to RECIST 1.1 criteria:

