5.5.6 Management of toxicity of olaparib (monotherapy treatment)

Any toxicity observed during the course of the study should be managed by interruption of the dose if deemed appropriate by the investigator. Repeat dose interruptions are to be allowed as required, for a maximum of 4 weeks (28 days) on each occasion. Olaparib must be interrupted until the patient recovers completely or the toxicity reverts to National Cancer Institute (NCI) Common Terminology Criteria for Adverse Events (CTCAE version 3) grade 1 or less.

Where toxicity reoccurs following re-challenge with olaparib and where further dose interruptions are considered inadequate for management of toxicity, then the patient is to be considered for dose reduction or must permanently discontinue treatment with olaparib.

Treatment must be interrupted if any NCI-CTCAE grade 3 or 4 adverse event occurs which the investigator considers to be related to administration of olaparib. If this has not resolved to at least NCI-CTCAE grade 1 during the maximum 4 weeks (28 days) dose interruption period, and/or the patient has already undergone a maximum of 2 dose reductions already, (to a minimum dose of 100 mg bd), the patient must permanently discontinue treatment with olaparib. If toxicity is appropriately resolved, then the patient should restart treatment with olaparib, but with a 50% dose reduction according to [Table 3](#). If the event recurs with the same severity, treatment should be interrupted again and, on resolution, a further dose

reduction made. If, on restarting treatment, the event continues to occur, the patient must permanently discontinue olaparib.

An exception to the management of olaparib-related toxicity is the occurrence of leukopenia and/or anaemia. In this case, the AE should be managed as deemed appropriate by the investigator (growth factor, transfusions), without interruption in study drug or change in dose. However, growth factors must be discontinued once the AE has recovered to grade 1 or better. They may be resumed, if necessary, if leukopenia/anaemia develops again and discontinued once it recovers.

The dose of olaparib must not be adjusted under any other circumstances unless the AstraZeneca physician gives prior agreement. Once the dose of olaparib has been reduced under no account should it be re-escalated.

All dose reductions and interruptions (including any missed doses), and the reasons for the reductions/interruptions are to be recorded in the eCRF.

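### For an olaparib-related grade 3–4 event still unresolved after 28 days, Section 5.5.6 requires permanent discontinuation, while the Section 5.8 bullet makes it optional and permits dose reduction without requiring resolution

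*Protocol*

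**What the plan says.** Protocol Section 5.5.6 (management of toxicity) sets a general rule first: "Olaparib must be interrupted until the patient recovers completely or the toxicity reverts to" CTCAE grade 1 or less. On length it says: "Repeat dose interruptions are to be allowed as required, for a maximum of 4 weeks (28 days) on each occasion". For grade 3 or 4 events that the investigator considers related to olaparib, interruption is compulsory. The section continues: "If this has not resolved to at least NCI-CTCAE grade 1 during the maximum 4 weeks (28 days) dose interruption period", and/or if two dose reductions have already been made, then "the patient must permanently discontinue treatment with olaparib. If toxicity is appropriately resolved, then the patient should restart treatment with olaparib" at half the dose, following Table 3 (400 to 200 to 100 mg bd). Leukopenia and anaemia are excepted and are managed without interruption or dose change. Any other dose adjustment needs the sponsor physician's prior agreement.

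Protocol Section 5.8 (discontinuation of investigational product) opens: "Patients may be discontinued from investigational product(IP), olaparib, in the following situations". One listed situation is "Any CTC grade 3 or 4 events that have not reverted to CTC grade 1 or less within 4 weeks (28-days"). The same bullet then leaves a choice to the investigator, saying that "following dose interruption, patients may be considered for dose reductions providing they have not already undergone the maximum number of dose reductions allowed", and refers to Section 5.5.6 for guidelines. It ends with a mandatory stop if, on re-challenge at "the lowest reduced dose, 100 mg bd (for guidelines refer to Section 5.5.6), any CTC grade 3 or 4 adverse events recur".

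Sections 6.2.2 and 6.2.3.1 cite Section 5.8 for the discontinuation criteria.

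**The concern.** Both sections use the same thresholds, grade 1 or less and 28 days, but attach different consequences to missing them. In 5.5.6 the patient must stop for good. In 5.8 the patient may stop, and the next sentence offers dose reduction as an alternative. The only kind of event that the bullet has named by then is one that has not reverted, so as written the discretion attaches to unresolved events.

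What is at stake is whether a patient with persistent, drug-related severe toxicity can be put back on olaparib. The case is realistic. Section 1.1.9 names bone marrow as the target organ of toxicity, Section 1.1.10 reports that thrombocytopenia has sometimes been grade 3 or 4, and the exception in 5.5.6 does not cover thrombocytopenia. The study has no independent data monitoring committee (Sections 3.1 and 12.4), so it relies on its written stopping rules being clear.

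**Working it through.** No statistical calculation applies: the protocol gives no figure here to reproduce. The check is a comparison of the two texts for one defined case, an olaparib-related grade 3 or 4 event, not leukopenia or anaemia, still above grade 1 when the 28-day interruption ends.

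1. *Is non-resolution enough by itself under 5.5.6?* Yes. The two triggers, non-resolution and two reductions already used, are joined by and/or, so either is sufficient.
2. *Does 5.5.6 leave any route to a reduced dose for this patient?* Not within its own scheme. Restart at half dose is given only for toxicity that has resolved. Anything else falls under the rule on the sponsor physician's prior agreement.
3. *Does the 5.8 bullet cover this patient?* Yes. It covers any grade 3 or 4 event, related or not, so the related event is included.
4. *What does the 5.8 bullet require?* Its lead-in is permissive. The conditions it states for a reduction are that an interruption has taken place and that the maximum number of reductions has not been used. Its only *must* concerns recurrence at 100 mg bd.
5. *Is there a rule of precedence?* None was found. Section 9.4 ranks the protocol against the clinical study agreement, but nothing ranks 5.5.6 against 5.8.

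Set out by reductions already used (the maximum of two comes from 5.5.6 and Table 3), with the event unresolved at day 28:

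| Reductions used | Current dose | Section 5.5.6 | Wording of the 5.8 bullet |
|---|---|---|---|
| 0 | 400 mg bd | permanent discontinuation | reduction may be considered |
| 1 | 200 mg bd | permanent discontinuation | reduction may be considered |
| 2 | 100 mg bd | permanent discontinuation | no further reduction |

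On dose reduction the wording conflicts in 2 of the 3 states. This counts logical cases, not patients. The protocol gives no rate of unresolved related grade 3 or 4 events, so no expected number can be derived.

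**The case against.** The strongest reply is that 5.8 was never meant to stand by itself. Its dose-reduction sentence refers to 5.5.6 for guidelines, and the next sentence does so again. The bullet gives neither the maximum number of reductions nor the 200 mg bd step. Both are found only in 5.5.6 and Table 3, so anyone acting on the bullet has to open the section that says the patient must stop. An interruption under 5.5.6 lasts until recovery or grade 1, so the bullet's mention of a preceding interruption can be read as implying resolution. The language of re-challenge and recurrence points the same way. A permissive lead-in is also natural for a mixed list: it covers objective progression, after which Section 3.1 says that patients will discontinue, and grade 3 or 4 events unrelated to olaparib, for which 5.5.6 sets no compulsory stop.

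Much of this stands. It shows what the authors probably intended, and it makes an unsupported re-challenge unlikely at a site that follows the reference. It does not remove the contradiction. The two references can be read as pointing to the dose steps, and neither states the resolution condition. The interruption in question is also capped at 28 days, so it can end without resolution, which is the very case the bullet opens with. A reader who does follow the reference meets a *must* that contradicts the *may*.

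A reader might infer something stronger: that Sections 6.2.2 and 6.2.3.1 send sites to 5.8 alone, so that sites would re-challenge unresolved toxicity on the investigator's sole authority. The documents do not support that. Those sections cite 5.8 but do not exclude 5.5.6, and 6.2.3.1 says that patients *should* be discontinued when a criterion is met. A reduction outside the 5.5.6 scheme also needs the sponsor physician's prior agreement.

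**Conclusion.** Wrong as written: an internal contradiction in a safety stopping rule, of minor severity. For a related grade 3 or 4 event unresolved at 28 days, 5.5.6 makes permanent discontinuation mandatory on that ground alone. The 5.8 bullet makes it optional and allows reduction to be considered without stating that resolution must come first. The cross-references and the sponsor-physician rule limit the risk but do not settle which text governs.

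This conclusion is confined to events that the investigator considers olaparib-related, with leukopenia and anaemia excluded, because only there do the two rules meet. The number of patients affected is unknown. No endpoint, estimate or analysis set is shown to be affected, and none should be inferred.

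**What to change.** Reword the Section 5.8 bullet so that it does the following:

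- Keeps any grade 3 or 4 event not back to grade 1 or less within 28 days as a reason for which a patient may be discontinued. Restricting the bullet to related events would drop the present 28-day criterion for unrelated ones.
- Adds that, if the event is olaparib-related, the patient must permanently discontinue, with leukopenia and anaemia managed as in Section 5.5.6.
- States that dose reduction per Table 3 may be considered only after resolution to grade 1 or less within 28 days, and only if fewer than two reductions have been used.
- Keeps the existing mandatory stop for recurrence at 100 mg bd.

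The cost is one reworded bullet and a notification to sites, handled under Section 8.5. It adds no visits, procedures or patients.

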5.8.1 Procedures for discontinuation of a patient from investigational product

A patient that decides to discontinue investigational product will always be asked about the reason(s) for discontinuation and the presence of any adverse events. If possible, they will be seen and assessed by an investigator(s). Adverse events will be followed up (see sections 6.4.3 and 6.4.4), study drug should be returned by the patient.

Any patient discontinuing investigational product should be seen at 30 days post-discontinuation for the evaluations outlined in the study schedule. The patient's tumour status should be assessed clinically and, if appropriate, disease progression should be confirmed by radiological assessment. After discontinuation of study medication, the principal investigator/sub-investigator will perform the best possible observation(s), test(s) and evaluation(s) as well as give appropriate medication and all possible measures for the safety of the patient. In addition, they will record on the eCRF the date of discontinuation, the reasons, manifestation and treatment at the time of discontinuation. If patients discontinue study treatment, the AstraZeneca monitor must be informed immediately. Patients will be required to attend the treatment discontinuation visit. The patient should return all study medication.

After discontinuation of the study medication at any point in the study, all ongoing AEs or SAEs must be followed until resolution unless, in the investigator's opinion the condition is unlikely to resolve due to the patients underlying disease, or the patient is lost to follow up (see Sections 6.4.3 and 6.4.4). All new AEs and SAEs occurring during the 30 calendar days

after the last dose of study medication must be reported (if SAEs, they must be reported to AstraZeneca within 24 hours as described in Section 6.4.4) and followed to resolution as above. Patients should be contacted at least 30 days after discontinuing study medication to collect and /or complete AE information. Any untoward event occurring subsequent to the 30-day follow-up AE reporting period that the investigator assesses as possibly related to the study medication should also be reported as an AE.

Any patient, who has not yet shown objective disease progression at withdrawal and not commenced subsequent anti-cancer therapy should continue to be followed as per RECIST 1.1 as detailed in section 6.2.3.4.

All patients must be followed for survival, unless they withdraw consent, up to the point at which the study is closed ie, 6-months after the last patient was first dosed.

If a patient is withdrawn from study, see Section 5.9.

5.9 Withdrawal from study

Patients are at any time free to withdraw from study (investigational product and assessments), without prejudice to further treatment (withdrawal of consent). Such patients will always be asked about the reason(s) and the presence of any adverse events. If possible, they will be seen and assessed by an investigator. Adverse events will be followed up (See Sections 6.4.3 and 6.4.4), and study drug should be returned by the patient.

Reasons for withdrawal from the study:

- Voluntary withdrawal by the patient who is at any time free to discontinue their participation in the study, without prejudice to further treatment
- Risk to patients as judged by the investigator and/or AstraZeneca
- Severe non-compliance with the protocol as judged by the investigator and/or AstraZeneca
- Incorrectly enrolled patients ie, the patient does not meet the required inclusion/exclusion criteria for the study
- The patient becomes pregnant
- Patient lost to follow-up

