5.2.1 Procedures for randomisation (Not Applicable)

5.3 Procedures for handling patients incorrectly enrolled

Patients who fail to meet the inclusion/exclusion criteria should not, under any circumstances, be enrolled or receive study medication. There can be no exceptions to this rule.

Where patients that do not meet the selection criteria are enrolled in error or incorrectly started on treatment, or where patients subsequently fail to meet the study criteria post-initiation, a discussion should occur between the AstraZeneca Study Delivery Team Physician and the investigator regarding whether to continue or discontinue the patient from treatment. Once a

decision is made, investigators need to ensure they comply with all applicable requirements for human patient protection and ethical review.

The AstraZeneca Study Delivery Team Physician is to ensure all such decisions are appropriately documented. In situations where an agreement cannot be reached, the patient should have their study therapy stopped and be withdrawn from the study.

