6.2.2 On-trial assessments

Olaparib is self-administered by the patient twice daily as instructed continuously. The visit schedule is based on 28 days periods. Patients will attend the clinic on days 1 (1st day of treatment), 8, 15, 29, 57 and every 28 days thereafter and the following assessments will be performed at time points specified in the study schedule (see [Table 2](#))

- Physical examination, including ECOG performance status and vital signs every visit
- ECG on Day 57 only (ie, +8 weeks from starting study treatment)
- Haematology, clinical chemistry and urinalysis
- Serum or urine pregnancy test for women of childbearing potential (prior to treatment on day of first treatment)
- AEs/SAEs and concomitant medications
- Disease-specific tumour marker where appropriate (CA-125, CA15.3, PSA, CEA etc)
- Tumour assessments (scans of the appropriate anatomical area applicable to the tumour under investigation and other sites as clinically indicated for assessment of disease by CT/MRI) every 8 weeks after day 1. Note that, after 6 months on study treatment, the scanning frequency can be increased to every 12 weeks.

Patients will continue with olaparib until radiological objective disease progression by RECIST 1.1 or as long as in the investigator's opinion they are benefiting from treatment and they do not meet any other discontinuation criteria as outlined in Section 5.8. Once patients on olaparib have been discontinued from treatment, other treatment options will be at the discretion of the investigator.

Patients will be evaluated until objective disease progression by RECIST or commencement of subsequent anti-cancer therapy, as per the study schedule (see [Table 2](#)), and then followed for survival, regardless of whether study treatment is discontinued or delayed and/or protocol violations, unless they withdraw consent. A repeat scan is needed at the next scheduled tumour assessment (at least ≥ 4 weeks) for confirmation of a PR and CR by RECIST 1.1.

The imaging modalities used for RECIST assessment will be CT or MRI scans of the relevant sites clinically indicated for assessment of disease. Any other sites at which new disease is suspected should also be appropriately imaged. Clinical examination (eg, photography of skin lesions) is acceptable for assessment of non-target lesion response.

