12.1.1 Efficacy analysis set

The efficacy analysis (Full Analysis Set) will follow the intention to treat (ITT) principle and will include all enrolled patients who take at least one dose of olaparib. The efficacy outcome variables will be summarised using the Full Analysis Set.

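### Sections 5.9 and 5.3 allow withdrawal from the study for reasons other than withdrawal of consent and then provide only for adverse-event follow-up and drug return, while 5.8.1 and 6.2.2 keep such patients in RECIST and survival follow-up

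*Protocol*

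**What the plan says.** **Withdrawal from the study.** Protocol Section 5.9 opens with the patient's own choice: "Patients are at any time free to withdraw from study (investigational product and assessments), without prejudice to further treatment (withdrawal of consent". It then provides for adverse-event follow-up and return of study drug, and gives a list of reasons for withdrawal from the study. Two of the six are voluntary withdrawal and loss to follow-up. The other four are not withdrawal of consent:

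- "Risk to patients as judged by the investigator and/or AstraZeneca"
- severe non-compliance
- "Incorrectly enrolled patients ie, the patient does not meet the required inclusion/exclusion criteria for the study"
- pregnancy

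Section 5.3 says that, when sponsor physician and investigator cannot agree on an incorrectly enrolled patient, "the patient should have their study therapy stopped and be withdrawn from the study".

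**Follow-up.** Section 5.8.1 says: "All patients must be followed for survival, unless they withdraw consent, up to the point at which the study is closed". The same section keeps patients who stop drug without progression or new anti-cancer therapy on RECIST follow-up. Section 6.2.2 has patients evaluated until progression or new therapy and then followed for survival, "regardless of whether study treatment is discontinued or delayed and/or protocol violations, unless they withdraw consent".

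**Analysis.** Under Section 12.1.1 the FAS "will include all enrolled patients who take at least one dose of olaparib", and Section 12.2.1 makes the FAS the denominator of the primary response rate.

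**The concern.** A site that has dosed an ineligible or severely non-compliant patient can read two different instructions. Under 5.9 the patient may be withdrawn from the study, and nothing there provides for further scans or survival contact. Under 5.8.1 and 6.2.2 both continue, and a protocol violation is expressly no reason to stop them.

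The primary endpoint needs a response confirmed on a later scan, so a patient who leaves before confirmation counts as a non-responder in the FAS. PFS is then censored at the last scan that could be evaluated (at day 0 if the patient is alive with no follow-up scan), and OS at the last date known alive. Withdrawal for risk or severe non-compliance may go with toxicity or decline, so that censoring may be informative. Scans and contacts that were never made cannot be recovered by a later analysis plan. That is why the point belongs in the protocol.

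**Working it through.** **Step 1. The passages side by side**

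| Reason | Treated as stopping drug | Treated as leaving the study |
|---|---|---|
| Severe non-compliance | 5.8 | 5.9 |
| Pregnancy | 13.3.1; Table 1 footnote | 5.9; 6.4.9.1 |
| Incorrect enrolment | 5.3, one possible result of the sponsor-investigator discussion | 5.9; 5.3 if no agreement |
| Risk to the patient | not listed in 5.8 under that name | 5.9 |

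The first column leads to 5.8.1, hence to RECIST and survival follow-up. The second leads to 5.9, which mentions only adverse events and drug return. Section 5.8.1 refers withdrawn patients to 5.9 without saying which rule prevails. Incorrect enrolment and severe non-compliance are protocol violations, so 6.2.2 covers them directly.

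**Step 2. When a response can be confirmed**

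Scans are every 8 weeks. Section 11.1.1 requires confirmation at least 4 weeks after the first response, and Appendix C (Section 5) plans it at the next scheduled scan, 8 weeks on. On schedule, confirmation therefore comes no earlier than about 8 + 8 = 16 weeks. A response confirmed before withdrawal still counts.

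**Step 3. Size for the primary rate**

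The protocol has no figure of its own to reproduce here: it gives no withdrawal rate and, by Section 12.3, no formal sample size calculation.

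Inputs:
- True response rate p: 11/27 = 40.7% and 11/33 = 33.3%, the confirmed rates in the two earlier studies at 400 mg bd (Section 1.2). These are for illustration only.
- Share w leaving under these reasons before confirmation: 2% to 5%. This is an assumption. In 150 patients it is 3 to 7.5.

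If those who leave would have responded at rate p but count as non-responders, the FAS rate is p(1 − w), and the shift is −p·w.

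| p | w | FAS rate | Shift (points) |
|---|---|---|---|
| 33.3% | 2% | 32.6% | −0.7 |
| 33.3% | 5% | 31.6% | −1.7 |
| 40.7% | 2% | 39.9% | −0.8 |
| 40.7% | 5% | 38.7% | −2.0 |

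For scale, the exact 95% CI at 50/150 = 33.3% is 25.9% to 41.5%. At 7/20 = 35% it is 15.4% to 59.2%. In a 20-patient group, one lost patient costs 1/20 = 5 points if that patient would have responded. The expected cost is 33.3%/20 = 1.7 to 40.7%/20 = 2.0 points.

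**Step 4. PFS and OS**

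The direction and size of any bias depend on why and when patients leave. The protocol does not allow either to be computed.

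**The case against.** A reader might infer that 5.9 requires ineligible, non-compliant, at-risk and pregnant patients to be taken off every study assessment, and for outcome-related reasons. The protocol does not support that, for four reasons.

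- The words about leaving product and assessments stand in the sentence on the patient's own withdrawal of consent, which 5.8.1 and 6.2.2 also except. They reach the listed reasons only if the section is read as a whole.
- Section 5.9 lists reasons and does not mandate removal. Section 5.3 withdraws an incorrectly enrolled patient only when no agreement is reached, and the sponsor takes part in that decision.
- Adverse-event follow-up continues under 5.9.
- Only risk and part of severe non-compliance are plausibly related to outcome. Ineligibility and pregnancy are not evidently so. Much toxicity and decline would leave through 5.8 (adverse event, unresolved grade 3 or 4 event, progression), which leads to continued follow-up.

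It can also be said that the follow-up rules are explicit and repeated: Sections 6.2.3.4 and 6.3.2 also continue RECIST follow-up. The study is exploratory and descriptive, so no decision threshold is at risk, and the shift in the response rate can only be downward.

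All of this stands, and it limits the size of the point. It does not remove the conflict. No passage says that scans and survival contact continue after a 5.9 withdrawal that is not withdrawal of consent, and two of the reasons are classified differently in different sections.

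**Conclusion.** The protocol gives inconsistent follow-up rules for dosed patients who stop because of incorrect enrolment, severe non-compliance, risk or pregnancy. The inconsistency should be removed.

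The likely effect on the primary response rate is small, about 0.7 to 2.0 points downward. That rests on an assumed 2-5% leaving, on all of them leaving before confirmation, and on their otherwise responding at the rates of the earlier studies. It is well inside the sampling uncertainty at 150 patients. The greater worry is early censoring of PFS and OS, which may be informative for risk and severe non-compliance. Its size cannot be derived from the protocol.

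**What to change.** Keep the change to data collection. State in 5.9 and 5.3 that patients who stop for any reason other than withdrawal of consent or loss to follow-up continue survival follow-up, and RECIST follow-up on the terms of 5.8.1 and 6.2.2. Align 5.3, 5.8, 5.9, 6.2.2, 6.4.9.1 and 13.3.1, so that severe non-compliance and pregnancy each have one classification throughout.

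When treatment stops, and how pregnant or at-risk patients are managed and imaged, is for the sponsor to reconcile across these passages. No rule is proposed here.

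The cost is protocol wording, plus follow-up that 5.8.1 and 6.2.2 already require.
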